4.7.4 Missing data

In general, missing data will not be imputed (except for dates) and the data will be analyzed according to the complete case approach. Proportion of missing data will be provided for all variables during descriptive analyses.

4.8 QUALITY CONTROL

After formal agreement of participation, centers will be trained in the protocol's procedures by a designated Clinical Research Associate. The frequency of subsequent contacts (monitoring on center visits, phone or e-mail) with the centers will be decided with the Sponsor and will be adapted if specific difficulties are identified during the training. A study monitoring plan, including for-cause monitoring, that is appropriate for the study design will be developed and implemented. Data QC will be performed remotely and at the center level, where permissible according to local regulations, by qualified designated personnel under professional secrecy.

Taking into account the context of the COVID-19 pandemic, no additional sanitary restrictions will be necessary other than the measures already set up at participating centers to ensure patient safety.

To ensure compliance with relevant regulations, data generated by this study must be available for inspection upon request by representatives of national authorities, and local health authorities as applicable, the Sponsor and representatives, and the IRB/IEC for each study center. The investigator will permit authorized representatives of the Sponsor, the respective national or local health authorities, and auditors to inspect facilities and records relevant to this study.

The Sponsor or representative CRO is responsible for verifying the eCRFs at regular intervals throughout the study to verify adherence to the protocol and the Sponsor or representative CRO applicable SOPs, completeness, accuracy and consistency of the data, and adherence to the Good Pharmacovigilance Practice (GVP): Module VI – Collection, management and submission of reports of suspected adverse reactions to medicinal products (EMA/873138/2011Rev 2), ICH GCP (ICH E6) and local regulations on the conduct of clinical research. Source data to be reviewed during this study will include but will not be restricted to: patient medical files, patient questionnaires (if applicable), patient's original laboratory test, histology, and pathology reports. All key data must be recorded in the patient hospital notes.

During and/or after completion of the study, quality assurance auditor(s) named by the Sponsor or the regulatory authorities may wish to perform on-center audits. The investigator will be expected to cooperate with any audit and provide assistance and documentation (including source data) as requested.

The Sponsor representatives are responsible for contacting and visiting the investigator for the purpose of inspecting the facilities and, upon request, inspecting the various records of the clinical study (eg, eCRFs and other pertinent data) provided that patient confidentiality is respected.

The investigator agrees to cooperate with the monitors to ensure that any problems detected in the course of these monitoring visits, including delays in completing CRFs, are resolved.

 Pierre Fabre TEMP CQA 0092 V 2.0 Owning site : CORPORATE QA	Template to use for writing Corporate document, except Corporate policy and form, WORD in english	Page 24/ 29
---	--	-------------

4.9 STUDY MANAGEMENT

Pierre Fabre is the Sponsor of the study. The Sponsor will be responsible, among others, for:

- Initiating, managing, and financing the study
- Selecting the qualified Principal Investigators
- Providing necessary information to the study centers to allow them to successfully conduct the study
- Obtaining the investigator agreement from all participating study centers
- Ensuring that the required regulatory approvals / favorable opinions are received
- Ensuring that any modifications required by the ethics committee or regulatory authority are implemented
- Performing and documenting root cause analysis and implementing appropriate corrective and preventive actions if non-compliance significantly affects or has the potential to significantly affect subject protection or reliability of clinical study results
- Ensuring that study procedures comply with applicable regulation for data protection.

4.10 LIMITATIONS OF THE RESEARCH METHODS

The biggest strength of this study is that it will be able to yield data on the utilization of neratinib and its effectiveness in real-life conditions of use and in the current treatment landscape, and in a more varied profile of patients (for example, those with more advanced disease or with certain comorbidities) than those who were evaluated as part of the pivotal ExteNET trial.

However, an observational and retrospective study comes with its limitations which are as follows:

1. Selection bias: Patients (or their next of kin/legal representative) who refuse to participate may limit the representativeness of the study results. Confounding can occur due to unobservable characteristics of patients. Even though a screening log would be established to record the details of patients who received neratinib as part of the EAP in Europe, irrespective of study inclusion status, it would only record patient demographic characteristics. Investigators will be asked to prospectively enroll consecutive patients who meet the eligibility criteria.
2. Retrospective design: since all data in the study will be extracted from past medical records, investigators will have no control over how the data was recorded and managed prior to the study. Furthermore, this retrospective design implies limited control over the exposure (neratinib treatment), covariates and potential confounders.
3. Attrition bias: Patients lost to follow-up and patients who withdraw their consent will be the main source of attrition bias in this observational study. This can threaten sample representativeness if too many patients are lost to follow-up or if they differ from those who are continuing follow-up. Should the proportion of patients lost to follow-up be non-negligible, the target precision will not be reached. To minimize any risks and potential impact, efforts will be undertaken to collect the data from the lost-to-follow-up patient's most recent visit. Baseline characteristics of patients lost-to-follow-up/withdrawn and those who completed the study may be compared, to evaluate representativeness.
4. Missing data: Depending on physician practices, some data might not be systematically measured or available (such as data on AEs). Missing data can bias the descriptions if it is not completely random. Even in cases where missing data is truly random, a potential impact on the precision of

 Pierre Fabre TEMP CQA 0092 V2.0 Owning site : CORPORATE QA	Template to use for writing Corporate document, except Corporate policy and form, WORD in english	Page 25/ 29
--	--	-------------

the estimates cannot be overlooked. Remote Monitoring procedures will be implemented, wherein it will be ensured that the eCRFs have been comprehensively filled. Sensitivity analyses may be carried out, where applicable, to estimate the impact of missing data on the study's outcomes. Furthermore, if a non-negligible proportion of missing data is observed for a certain parameter, groups of patients with and without missing data may be compared.

5. Heterogeneity between study centers: since this is an observational study of real-life neratinib use in the context of a European EAP, prescription modalities and patient follow-up schedules can vary widely based on standard practices in each country and/or investigating center. This could lead to an over or under-reporting of certain data (such as AEs). Where deemed appropriate subgroup analyses by country could be performed for certain outcomes or variables of interest.

Further details on how biases in the study design are to be addressed will be elaborated in the SAP.

5 PROTECTION OF HUMAN SUBJECTS AND LOCAL REGULATORY ASPECTS

The study will be conducted in accordance with the ethical principles of the declaration of Helsinki and the General Data Protection Regulation (UE 2016/679) and other local regulatory requirements. The need to submit the protocol to an Institutional Review Board/Independent Ethics Committee (IRB/IEC) and the requirement of informed consent will be considered in accordance with local law. Any amendments to the study protocol, as well as the associated ICF will be submitted to the appropriate IRB/IEC for approval prior to implementation, according to the requirement of each IRB/IEC.

This observational study does not involve any changes in the local care standards of the patients participating in the study, does not compromise their physical or psychological integrity and does not require any special follow-up visits for these patients. Each patient will be fully informed before enrollment in the study and start of data abstraction, and their written consent or verbal non-opposition will be taken, as per the local regulations of each target country. Wherever applicable, an ICF waiver will be obtained, depending on approval by Ethics Committees and/or local regulations.

Investigators shall ensure that personal identifiers will be removed from any study files that are accessible to non-study personnel in accordance with applicable laws and regulations. In case of sub-contracting, it is the responsibility of the service provider concerned to ensure that computerized processing is in conformity with the applicable national regulations regarding the protection of personal data and, if necessary, carry out any formality with the supervisory authorities and transmit the declaration date to Sponsor.

The investigator must ensure that patient confidentiality is maintained. It is required that the investigator and institution permit authorized representatives of the Sponsor, of the regulatory agency(s), and the institutional ethics committees' direct access to review the patient's original medical records for verification of study-related procedures and data. Direct access includes examining, analyzing, verifying, and reproducing any records and reports that are important to the evaluation of the study. Access to the patient's medical file is to be granted under the supervision and responsibility of the principal investigator or their center personnel. The investigator is obligated to inform and obtain the consent of the patient to permit named representatives to have access to their study-related records without violating the confidentiality of the patient. The study will be registered on ClinicalTrials.gov and will be in national registries where applicable.

 Pierre Fabre TEMP CQA 0092 V2.0 Owning site : CORPORATE QA	Template to use for writing Corporate document, except Corporate policy and form, WORD in english	Page 26/ 29
--	--	-------------

6 MANAGEMENT AND REPORTING OF ADVERSE EVENTS/ADVERSE REACTIONS

This is a retrospective, observational, longitudinal study. As this is a study based on secondary use of data from the EAP, it will not be necessary to collect and transmit the AEs/adverse reactions data to Pierre Fabre Pharmacovigilance team. The system of Pharmacovigilance data collection from the EAP is already put in place prospectively. Therefore, safety data are already recorded in the Pierre Fabre Pharmacovigilance safety database, reported, and analyzed.

According to the study objectives, data on relevant AEs will be collected and analyzed. Relevant AEs will be defined as all SAEs or AEs leading to dose adaptation or treatment discontinuation, and AEs of interest. The following are some AEs of interest: occurrence of diarrhea (onset/resolution dates, maximum grade, actions taken), gastro-intestinal toxicity (nausea, vomiting, abdominal pain, constipation), hepatic disorders, cardiac disorders, pulmonary disorders, pancreatitis, and reproductive and developmental disorders.

7 PLANS FOR DISSEMINATING AND COMMUNICATING STUDY RESULTS

Data will be analyzed and presented in a final report which will be submitted to the Sponsor. This final report will help in the preparation of one or more publications.

Any written or oral communication of the research results will receive prior consent of the Sponsor and, if necessary, of any committee formed for the research. All publications will follow the International Committee of Medical Journal Editors (ICMJE, 2010) guidelines. In addition, communication in appropriate scientific meetings will be considered.

8.2 OWNERSHIP OF RESULTS

The results of the Study shall be owned exclusively by PIERRE FABRE MEDICAMENT's and PIERRE FABRE MEDICAMENT and/or any designee shall have free use of the same in France and worldwide.

Such ownership shall apply to any data, patentable or non-patentable inventions, know-how and any invention resulting from the Study.

 Pierre Fabre TEMP CQA 0092 V2.0 Owning site : CORPORATE QA	Template to use for writing Corporate document, except Corporate policy and form, WORD in english	Page 28/ 29
--	--	-------------

1 ABBREVIATIONS

Abbreviation	Definition
AE	Adverse Event
AJCC	American Joint Committee on Cancer
CI	Confidence Interval
CISH	Chromogenic in Situ Hybridization
CNS	Central Nervous System
DDFS	Distant Disease-Free Survival
DTR	Distant Tumor Recurrence
EAP	Early Access Program
eCRF	Electronic Case Report Form
ECOG	Eastern Cooperative Oncology Group
EOB	End of Observation
ENR	Enrolled Set
ER	Estrogen Receptor
FAS	Full Analysis Set
FISH	Fluorescence in Situ Hybridization
HER2	Human Epidermal Growth Factor Receptor 2
HR	Hormone Receptor
ICBCR	Invasive Contralateral Breast Cancer Recurrence
ICF	Informed Consent Form
iDFS	Invasive Disease-Free Survival
IHC	Immunohistochemistry

Document: ZZA65950_NEAR_SAP_v2.0

Author: [name]

Version Number: 2.0

Version Date: 22SEP2023

IIBTR	Invasive Ipsilateral Breast Tumor Recurrence
MedDRA	Medical Dictionary for Regulatory Activities
OS	Overall Survival
pCR	Pathologic Complete Response
PR	Progesterone Receptor
PT	Preferred Term
RIR	Regional Invasive Recurrence
RWS	Real World Solutions
SAE	Serious Adverse Event
SAP	Statistical Analysis Plan
SOC	System Organ Class
T-DM1	Trastuzumab Emtansine
TLFs	Tables/Listings/Figures

2 INTRODUCTION

This SAP describes the rules and conventions to be used in the presentation and analysis of patients with early-stage Human Epidermal Growth Factor Receptor-2 positive (HER2+) breast cancer, treated with neratinib as an extended adjuvant therapy in the context of the European Early Access Program (EAP). It describes the data to be summarized and analyzed, including specifics of the statistical analyses to be performed.

This SAP is based on protocol version 1.0, dated 23 September 2021.

3 STUDY OBJECTIVES

3.1 Primary Objectives

The primary objective is to describe the demographic and clinical profiles of patients with early-stage HER2+ breast cancer treated with neratinib as an extended adjuvant therapy as part of the EAP in Europe.

3.2 Secondary Objectives

The secondary objectives are:

- To describe neratinib treatment patterns including time to initiation of neratinib, dosing after trastuzumab-based treatment, treatment dose, treatment duration, permanent and temporary discontinuations, reasons for discontinuations, and concomitant treatments.
- To describe breast cancer treatment history before neratinib initiation, including all neoadjuvant and adjuvant therapies (in terms of agent name, dosage, and duration of use), surgeries and other interventions (type and outcome).
- To describe the frequency of relevant Adverse Events (AEs) in breast cancer patients using neratinib as an extended adjuvant therapy. Relevant AEs are defined as all Serious Adverse Events (SAEs) or AEs leading to dose adaptation or treatment discontinuation, and AEs of interest.

3.3 Exploratory Objectives

The exploratory objectives are:

- To describe the first recurrence patterns.
- To describe invasive disease-free survival (iDFS) in patients with early-stage HER2+ and Hormone Receptor-positive (HR+) breast cancer treated with neratinib as an extended adjuvant therapy, over the study observation period.
- To describe distant disease-free survival (DDFS) in patients with early-stage HER2+ and HR+ breast cancer treated with neratinib as an extended adjuvant therapy, over the study observation period.
- To describe the incidence of central nervous system (CNS) metastasis.
- To describe overall survival (OS) in patients with early-stage HER2+ and HR+ breast cancer treated with neratinib as an extended adjuvant therapy, over the study observation period.

[figure not shown]
4 STUDY DESIGN

4.1 General Description

This is a European, multi-country, multicenter, retrospective, observational, longitudinal study to describe the demographic characteristics and clinical profiles of patients with HER2+ breast cancer who were treated with neratinib as an extended adjuvant therapy, in the context of the EAP in Europe.

The target countries for patient enrollment will include Belgium, Croatia, France, Italy, and Spain.

A pictorial representation of the NEAR study scheme is provided in Figure 1 below.

Figure 1. The NEAR Study Scheme

4.2 Sample Size

Sample size calculation is not applicable, since the study plans to include all eligible breast cancer patients having received neratinib as an extended adjuvant therapy through the EAP in the target European countries. The number of patients is estimated to be up to 200 patients. Using the table below, the precision estimates for a 95% confidence interval (CI) were calculated around proportions ranging from 10% to 50% for a sample size between 150 and 300 patients (see Table 1).

A sample size of 200 patients would allow to assess a category of primary objective (demographic and clinical description of eligible patients) of 10%, 20%, 30%, 40% and 50% of patients with a precision of approximately $\pm 4.1\%$, $\pm 5.5\%$, $\pm 6.4\%$, $\pm 6.8\%$ and $\pm 6.9\%$, respectively.

Based on the feasibility, 120 patients would be enrolled instead of 200 patients originally planned.

A sample size of 120 or 100 patients would allow to assess a category of primary objective (demographic and clinical description of eligible patients) of 10%, 20%, 30%, 40% and 50% of patients with a precision of approximately $\pm 5.4\%$ or 5.9% , $\pm 7.2\%$ or 7.9% , $\pm 8.2\%$ or 9% , $\pm 8.8\%$ or 9.6% and $\pm 9\%$ or 9.8% , respectively.

Table 1 Precision estimates for 95% CI around proportions

Precision estimate*	Proportion				
	10%	20%	30%	40%	50%
Sample size	10%	20%	30%	40%	50%
100 patients	5.9%	7.9%	9%	9.6%	9.8%
120 patients	5.4%	7.2%	8.2%	8.8%	9%
150 patients	4.8%	6.4%	7.3%	7.8%	8.0%
200 patients	4.1%	5.5%	6.4%	6.8%	6.9%
250 patients	3.7%	4.9%	5.7%	6.1%	6.2%
300 patients	3.4%	4.5%	5.2%	5.5%	5.6%

*Precision estimates for a 95% CI were calculated using statistical analysis system (SAS) version 9.4 or higher (SAS Institute, Cary, NC, USA)

4.3 Patient Selection Criteria

Eligible patients will be selected among those having received at least one dose of neratinib for the treatment of early-stage HER2+ breast cancer in the EAP, between 01 August 2017 and 31 December 2020. Patients (or next of kin/legal representative, if applicable) who provide written informed consent form (ICF) or non-opposition to data collection, as per local regulations, will be enrolled.

4.3.1 Inclusion Criteria

Patients will be eligible for inclusion if they fulfil all the following criteria:

1. Age \geq 18 years at neratinib treatment initiation.
2. Patient diagnosed with HER+ breast cancer.
3. Having received at least one initial dose of neratinib as an extended adjuvant therapy for the treatment of early-stage HER2+ breast cancer, in the context of the EAP in Europe, and between 01 August 2017 and 31 December 2020.
4. Patients (or next of kin/legal representative, if applicable) who provide written informed consent or non-opposition.

Note: Given the retrospective nature of the study, for deceased or lost to follow-up patients, where a signed informed consent is required, the informed consent may be obtained from a next of kin / legal representative, or an ICF waiver will apply, depending on approval by Ethics Committees and/or local regulations.

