7 GENERAL CONSIDERATIONS

7.1 Patient Identification Period

The patient identification period is the eligibility time window for selection of patients who initiated neratinib treatment within the EAP in Europe between 01 August 2017 and 31 December 2020.

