7.5 Study Entry Date

The study entry date is defined as the cut-off date until when the eligible patients' data as obtained from medical charts are abstracted for analysis in the study. This date will be the same for all patients and corresponds to the date of first patient in, 05 July 2022.

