7.8 End of Observation (EOB) Date

The end of observation (EOB) date is defined as the study entry date, date of death or date of last contact, whichever happens first.

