7.10 Changes from Protocol

In the eCRF an additional inclusion criterium was considered, i.e., the patient was diagnosed with HER2+ breast cancer. For analysis proposes this additional criterium is considered in the analysis datasets and used in the identification of the FAS.

In the protocol the study entry date was defined as the cut-off date until when the eligible patients' data as obtained from medical charts are abstracted for analysis in the study. Based on a request from Pierre Fabre, the study entry date was assigned in the SAP to the date of first patient in, 05 July 2022, to ensure that all patients have the same cut-off date.

In section 8.2, two additional periods were considered in the time to event analysis, i.e., in protocol the intervals considered were 1, 3, 6, 9 and 12 and for analysis the periods that will be considered are 1, 3, 6, 9, 12, 15 and 18.

The subgroup analysis considered in section 8.4 has been updated from protocol. The nodal status at initial diagnosis and the tumor size at initial diagnosis were removed from the subgroups of interest. The subgroup previous adjuvant or neoadjuvant therapy was defined in the protocol as "Yes/ No" and will be updated to "Neoadjuvant + Post neoadjuvant treatment/ Adjuvant only".

The following subgroups analysis was added: according to EU label status, Concomitant Corrective Antidiarrheal, Concomitant Prophylaxis Antidiarrheal, Initial Dose of Neratinib.

In the protocol the exploratory analysis was planned to be performed only in HR+ patients, it will be analyzed separately for HR+ / HR- patients.

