13.2.4 Overall Survival

OS is defined as the time, in months, from neratinib initiation date (index date) until the date of death (due to any cause).

Table 7 Event and time details for CNS metastasis

Event	Type	Events and censoring dates
Death (all causes)	Uncensored	Date of death
Loss to follow-up	Censored	Date of EOB (section 7.8)
Withdraw consent	Censored	Date of EOB (section 7.8)
No event	Censored	Date of EOB (section 7.8)

OS in months, will be calculated as follows:

- For patients who have an event:
 - $(Date\ of\ death - Index\ date + 1) / 30.4$
- For patients who do not have an event (censored):
 - $(Last\ date\ known\ to\ be\ alive - Index\ date + 1) / 30.4$

Death and corresponding date will be identified from the “Survival Status” page of the eCRF.

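### OS deaths can enter only through next-of-kin or waiver routes, so the survival curves depend on capturing deceased and living patients equally, which the SAP does not check

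*SAP*

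**What the plan says.** - **Cut-off.** SAP 7.5 sets one study entry date: "This date will be the same for all patients and corresponds to the date of first patient in, 05 July 2022". SAP 7.10 lists this as a change from protocol, made at the sponsor's request so that all patients share a cut-off.
- **Follow-up.** Index dates fall "between 01 August 2017 and 31 December 2020" (SAP 7.1). Observation ends at "the study entry date, date of death or date of last contact, whichever happens first" (SAP 7.8). OS runs from the index date to death from any cause (SAP 13.2.4).
- **Entry of living patients.** Consent, refusal, non-opposition or opposition is documented before any data are abstracted (Protocol 4.2.2.2). In France a letter followed by four weeks without opposition is enough.
- **Entry of deceased or lost patients.** SAP 4.3.1 provides that "for deceased or lost to follow-up patients, where a signed informed consent is required, the informed consent may be obtained" from a next of kin or legal representative, or that a waiver applies, subject to ethics committee and local rules. The French letter may go to the next of kin.
- **Checks.** Protocol 4.2.2.2 has each centre log sex, age category and vital status (dead, alive or lost) for all eligible patients. Protocol 4.10 says the log holds demographic characteristics only, names refusal and attrition as sources of bias, and leaves the handling of bias to the SAP. SAP 10 tabulates survival status within the full analysis set. The SAP text has no comparison with the log, no summary of deaths by inclusion route and no sensitivity analysis on this point.

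**The concern.** Consent comes after the follow-up that is being analysed. A patient who consents for herself on or after 05 July 2022 was alive on that date, so her probability of an OS event inside the window is zero. The number of deaths in the analysis is then set by how many deceased patients could be brought in by next of kin or waiver, relative to how many living patients agreed. Those routes differ by country and by approval.

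If deceased patients are harder to include, survival looks too good. If a centre has a waiver for the deceased but needs signed consent from the living, survival can look too poor. SAP 13.2 pools all centres, so a reader of the OS curve cannot separate the disease from the enrolment rules. The Kaplan-Meier interval does not reflect this; with no deaths at all, the standard interval has zero width.

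**Working it through.** **1. The plan's own figure.** The only design calculation is the precision table in SAP 4.2. With half-width = 1.96 × √(p(1−p)/n) and n = 120, p = 10, 20, 30, 40, 50% gives 5.37, 7.16, 8.20, 8.77, 8.95 points. The SAP states 5.4, 7.2, 8.2, 8.8, 9, so it reproduces. The plan gives no OS rate or expected event count.

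**2. Length of the window.** By the SAP rule, (cut-off − index + 1)/30.4:
- index 01 August 2017: 1,800/30.4 = 59.2 months;
- index 31 December 2020: 552/30.4 = 18.2 months.

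The landmarks in SAP 8.2 run from 1 to 18 months. All of them lie in time that an own-consent patient must have survived. An analysis with delayed entry at consent would leave her no time at risk before the cut-off.

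**3. Effect of unequal capture.** Let q be the true proportion dead by the cut-off and r the capture rate of the deceased divided by that of the living. Apparent survival = (1−q)/[(1−q) + r·q]. Neither q nor r is in the documents; both are assumed.

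| r | q = 2% | q = 5% | q = 10% | deaths among 120 at q = 5% |
|---|---|---|---|---|
| 1 | 98.0% | 95.0% | 90.0% | 6.0 |
| 0.75 | 98.5% | 96.2% | 92.3% | 4.6 |
| 0.5 | 99.0% | 97.4% | 94.7% | 3.1 |
| 0.25 | 99.5% | 98.7% | 97.3% | 1.6 |
| 0 | 100% | 100% | 100% | 0 |

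Example: q = 5%, r = 0.5 gives 0.95/(0.95 + 0.025) = 97.4%.

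**4. The other direction.** Assume 200 eligible patients, 8 dead and 192 alive (4% dead), with 60% of the living enrolled. If all the deceased are included, the death share is 8/(8 + 115.2) = 6.5%. If 60% are included, it is 4.8/(4.8 + 115.2) = 4.0%, the truth.

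**5. Kaplan-Meier check by simulation.** Assumptions: exponential deaths with 5% dead at 36 months, and follow-up uniform from 18.2 to 59.2 months.

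| | 18 months | 36 months |
|---|---|---|
| True | 97.5% | 95.0% |
| r = 1 | 97.5% | 95.0% |
| r = 0.5 | 98.7% | 97.4% |
| r = 0.25 | 99.3% | 98.7% |
| r = 0 | 100% | 100% |

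**6. Against sampling error.** At 18 months, halving capture moves the estimate by 98.7 − 97.5 = 1.2 points. The 95% half-width at 97.5% with n = 120 is 1.96 × √(0.975 × 0.025/120) = 2.8 points.

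**The case against.** The plan intends to include every eligible patient in the programme, and the provision in SAP 4.3.1 exists so that deceased and lost patients are not left out. In any closed cohort with known vital status, those alive at the cut-off have survived to it; that alone biases nothing. The outcomes are descriptive, OS is exploratory, and the 1.2-point shift above is smaller than the sampling error. All of this stands, and it limits the point.

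It also rules out several stronger readings:

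- **Immortal time by construction.** A reader might infer that the pooled curve must be inflated. Step 5 shows otherwise: equal capture returns the true curve.
- **The cut-off as the cause.** A later cut-off would still leave the time from index to consent guaranteed. Setting it at first patient in makes that time the whole window and removes delayed entry as a remedy, but the source is consent after follow-up.
- **All events affected.** Recurrences in living patients still count in iDFS and DDFS (SAP 13.2.1 and 13.2.2). Only the death component is closed to own-consent patients.
- **Centres with living patients only.** No section identifies such a centre; local approval makes it possible.
- **Low enrolment as proof.** SAP 4.2 expects 120 patients instead of 200. That shows incomplete coverage, which may be due to non-participating centres, and says nothing about capture by vital status.

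What the objection does not answer is that equal capture is assumed and never examined, although the screening log would allow it.

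**Conclusion.** The point holds as survivor selection of unknown size and direction. Every OS death, and the death component of iDFS and DDFS, depends on next-of-kin consent or non-opposition or on a waiver. The pooled curves are right only if deceased and living eligible patients were captured at the same rate. Under an assumed 5% mortality, the error runs from 0 points (equal capture) through +2.4 (half) to +5.0 (none); it is negative where the deceased are captured more fully than the living.

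This rests on reading first patient in as the first consent or non-opposition, which the documents do not define. A French letter sent shortly before that date could be a small exception. The matter is worth correcting because publications are planned (Protocol 7), but it does not touch the primary objective.

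**What to change.** In SAP 13.2:

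1. Keep the pooled OS, iDFS and DDFS curves, and add a sensitivity curve for each that leaves out any centre whose approvals allowed only living patients to be enrolled. Ethics approvals identify these centres. Restricting the main result to waiver centres is not advised, because they can over-represent deaths (step 4).
2. Beside the curves, tabulate enrolled against eligible patients by vital status (dead, alive, lost) and country, from the screening log. Reconcile the two protocol descriptions of what the log holds.
3. If capture differs by vital status, add a sensitivity estimate weighted by the inverse of the inclusion proportion in each vital-status group. This cannot be computed where none of the deceased was included. The log fields listed do not include hormone receptor status, so the weights would have to be assumed common to HR+ and HR− patients.
4. State with the OS result that own-consent patients could not have an event before the cut-off.
5. Report deaths by inclusion route only where the route is recorded. SAP 10 mentions consent, non-opposition and waiver but does not show that own and next-of-kin consent are held separately.

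Cost: SAP wording, one extra table, and fewer patients with wider intervals in the sensitivity curves. If the database is already locked, Protocol 4.7.1 allows this to be reported as a documented deviation.
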